10.3 Monitoring

Due to the restrictions imposed on clinical and hospital visits by the COVID-19 pandemic, all monitoring of this study will be conducted remotely. Monitors will work with the Study Coordinator at each site to determine times for "joint" remote monitoring – meaning that the monitor and the SC will review data together over the telephone.

Remote monitoring will be conducted according to the applicable ICH and GCP guidelines to ensure protocol adherence, quality of data, drug accountability, compliance with regulatory requirements and continued adequacy of the investigational site and its facilities. The Investigator will cooperate in the monitoring process by ensuring the availability of the eCRFs, source documents and other necessary documents at the time of remote monitoring and by prompt attention to any matters brought to his/her attention by the monitor.

10.4 Audit

ICH guidelines for GCP require independent inspection of clinical program activities. Such inspections may be performed at any time - before, during and/or after the study. The Investigator and study staff are responsible for maintaining the site master file containing all study-related regulatory documentation as outlined by the Sponsor that will be suitable for inspection at any time by the Sponsor, its designees, and/or regulatory agencies. The Investigator understands and agrees to give access to the necessary documentation and files.

10.5 Retention of Data

All records connected with this clinical study will be retained for at least two years following the date of an approved marketing application [21 CFR 312.62(c)]; or at least three years from the formal discontinuation of favipiravir development; or seven years from the end of the study, whichever is longer. All local laws regarding retention of records must also be followed. Study sites are required to retain all records until written notification allowing destruction is received from the Sponsor.

11 ETHICS

11.1 Ethics Committee

A properly constituted, valid IRB/IEC must review the treatment plan and procedures, the Investigator's informed consent document, and related subject information. It is the responsibility of the Investigator to ensure that all aspects of institutional review are conducted in accordance with current regulations governing the jurisdiction where the study is conducted. The Sponsor (or designee) must receive a letter documenting IRB/IEC approval that specifically identifies the title of the treatment plan, subject information sheet, and ICF.

11.2 Subject Information and Consent

It is the responsibility of the Investigator to ensure that written informed consent is obtained from the subject or legal representative before any activity or procedure is undertaken that is not part of routine care. The informed consent must comply with local regulations.

The background of the study, the procedures, the potential benefits and risks of the treatment, and the fact that treatment is voluntary for the subject must be explained to the subject or legal representative. The subject or representative must be given sufficient time to consider whether to consider whether or not to participate in the study. A copy of the ICF, signed and dated by the subject/representative and the Investigator (or designee), must be given to the subject/representative. Confirmation of a subject's informed consent must also be documented in the subject's medical record prior to any treatment with favipiravir.

Each consent form should contain an authorization allowing the Investigator and the Sponsor (or designee) to use and disclose protected health information (PHI) (i.e., subject-identifiable health information) in compliance with local law. The signed consent form will be retained with the treatment records.

12 GENERAL CONSIDERATIONS

12.1 Discontinuation of the Study

The Sponsor reserves the right to discontinue the study at any time for any reason.

12.2 Use of Information and Publication

All information concerning favipiravir, Sponsor operations, patent applications, formulas, manufacturing processes, basic scientific data, formulation, and other information supplied by the Sponsor to the Investigator and not previously published is considered confidential and

remains the sole property of the Sponsor. The Investigator agrees to use this information only to treat this patient and will not use it for other purposes without written consent of the Sponsor.

The information obtained in this study will be used by the Sponsor in connection with the continued development and, if approved, commercialization of favipiravir. Thus, Sponsor may disclose such information as required to other clinical Investigators, contractors, and government regulatory agencies.

Publication or other public presentation of results from this study and related information is subject to the provisions of the Clinical Trial Agreement between Sponsor and the Study Site.

13 SCHEDULE OF ASSESSMENTS

ASSESSMENT	HOSPITALIZED							FOLLOW UP Outpatient or Hospitalized		
	DAY 1 PRE-DOSE	DAY 1 POST-DOSE	DAY 2	DAY 3	DAY 8	Day 11	DAY 14	DAY 15 (-1 to + up to 2 days)	DAY 29 ± 2 days	DAYS 45 and 60 ± 2 days ⁸
Informed Consent	X							• /		·
Medical/Surgical History	X									
Physical Exam 10	X									
Limited Physical Exam ³		X	X	X	X	X	X	X	X	X
Concomitant Medications Review ¹²	X		X	X	X	X	X	X	X	X
Review of Entry Criteria	X									
Vital Signs (BP, HR, Temp, Resp) ³	X	X	X	X	X	X	X	X	X	X
Clinical Laboratory Exams ^{1,2,,9}	X			X	X	X		X	X	
Blood for antibodies to SARS-CoV-2	X							X	X	
Blood for PK Sampling	X ⁴	X^4	X^5	X^6	X^5	X^6	X^5			
SpO2 by Finger Sensor ³	X	X	X	X	X	X	X	X	X	X
Urine or Blood Pregnancy Test	X									
Nasopharyngeal and Oropharyngeal Swabs for Viral RNA, PCR and TCID ₅₀	X			X ¹¹	X ¹¹	X ¹¹		X	X	
Clinical Status – 6-point Ordinal Scale ³	X		X	X	X	X		X	X	X
National Early Warning Score (NEWS2) ³	X		X	X	X	X		X	X	X

	DAY 1 PRE-DOSE	DAY 1 POST-DOSE	DAY 2	DAY 3	DAY 8	Day 11	DAY 14	DAY 15 (-1 to + up to 2 days)	DAY 29 ± 2 days	DAYS 45 and 60 ± 2 days ⁸
ECOG Performance Status ³	X		X	X	X	X	X	X	X	X
Study Specific Symptom Status ³	X		X	X	X	X	X	X	X	X
Randomization	X									
Investigational Product Dosing		Favipiravir Dosing Days 1-14 (1800 mg BID on Day 1000 mg BID Days 2-14) ⁷								
Solicitation of Treatment- Emergent Adverse Events ³		X	X	X	X	X	X	X	X	X
Release from the Study										X

- 1. Hematology, Chemistry (See Section 8.4).
- 2. May use results of labs taken at the hospital as part of SOC if done no more than 24 hours prior.
- 3. To be measured every day while hospitalized and at each clinic visit after hospital discharge through Day 60
 - a. Vital signs
 - b. Clinical Status 6-point scale
 - c. NEWS2
 - d. ECOG Performance status
 - e. Study-specific symptom status
 - f. Adverse Events
 - g. SpO2
 - h. Limited PE (heart and lungs)
- 4. PK on Day 1 prior to favipiravir dosing and between 45 to 75 minutes post-first dose.
- 5. PK trough samples to be taken approximately 30 minutes prior to any dose.
- 6. PK peak samples to be taken between 45 to 75 minutes post-dose
- 7. Maintenance dose for CP score A is 800 mg BID.
- 8. Days 45 and 60 may be completed in the hospital, outpatient clinic, or by phone
- 9. Subjects will undergo 9 planned venipunctures.
- 10. To be completed by PI or designee
- 11. Days 3, 8, 11 Nasopharyngeal and Oropharyngeal Swabs for Viral RNA, PCR and TCID₅₀ may be done +/- 1 day from their scheduled day. Swabs will also be obtained on day of discharge from hospital if discharge occurs before Day 15.
- 12. To be checked throughout hospitalization and at clinic visits and changes only recorded as applicable.

Appendix A: Subject Status Scales

1. ECOG Performance Status

GRADE

ECOG PERFORMANCE STATUS

- Fully active, able to carry on all pre-disease performance without restriction
- Restricted in physically strenuous activity but ambulatory and able to carry out work of a light or sedentary nature, e.g., light housework, office work
- Ambulatory and capable of all selfcare but unable to carry out any work activities; up and about more than 50% of waking hours
- Capable of only limited selfcare; confined to bed or chair more than 50% of waking hours
- 4 Completely disabled; cannot carry on any selfcare; totally confined to bed or chair
- 5 Dead

2. Study Specific Symptom Status Scale

Symptom	Present? Y/N	Severity:
		Mild, Moderate, Severe
Feeling Feverish		
Dyspnea		
Cough		
Use of Antibiotic		

## LIST OF ABBREVIATIONS AND DEFINITION OF TERMS

| Abbreviation | Definition                              |
|---------------------|--|
| AE                  | Adverse event                                  |
| ALT                 | Alanine transaminase                           |
| ANCOVA              | Analysis of Covariance                         |
| ANOVA               | Analysis of variance                           |
| AST                 | Aspartate transaminase                         |
| BCG                 | Bacillus Calmette-Guérin                       |
| BID                 | Twice daily                                    |
| CI                  | Confidence interval                            |
| COVID-19            | Coronavirus disease of 2019                    |
| CRF                 | Case report form                               |
| CSR                 | Clinical study report                          |
| CT                  | Computed tomography                            |
| CTCAE               | Common Terminology Criteria for Adverse Events |
| ECMO                | Extracorporeal membrane oxygenation            |
| ECOG                | Eastern Cooperative Oncology Group             |
| EDC                 | Electronic data capture                        |
| FCS                 | Fully conditional specification                |
| Fio2                | Fraction of inspired oxygen                    |
| ICH                 | International Council for Harmonisation        |
| ICU                 | Intensive care unit                            |
| IEC                 | Institutional Ethics Committee                 |
| IRB                 | Institutional Review Board                     |
| ITT                 | Intent-to-treat                                |
| LOCF                | Last Observation Carried Forward               |
| MAR                 | Missing at random                              |
| mITT                | Modified intent-to-treat                       |
| MedDRA              | Medical Dictionary for Regulatory Activities   |
| NEWS2               | National Early Warning Score 2                 |
| PaO2                | Pressure of oxygen                             |
| PCR                 | Polymerase Chain Reaction                      |
| PD                  | Pharmacodynamic(s)                             |
| PK                  | Pharmacokinetic(s)                             |
| PMM                 | Predicted mean Matching                        |
| PP                  | Per protocol                                   |
| Rel Day             | Relative study day                             |
| RM ANOVA            | Repeated measures analysis of variance         |

| Abbreviation | Definition   |
|---------------------|---|
| SAE                 | Serious adverse event                                       |
| SAP                 | Statistical analysis plan                                   |
| SARS-CoV-2          | Severe acute respiratory syndrome coronavirus 2             |
| SD                  | Standard deviation  |
| SOC                 | Standard of care  |
| SpO 2    | Oxygen saturation   |
| TCID 50  | Median Tissue Culture Infectious Dose at 50% cell infection |
| TEAE                | Treatment-emergent adverse event                            |
| TTCR                | Time to clinical recovery                                   |
| ULN                 | Upper limit of normal                                       |
| WHO                 | World Health Organization                                   |

## 1. INFORMATION FROM THE STUDY PROTOCOL

### 1.1. Introduction and Objectives

#### 1.1.1. Introduction

Favipiravir is a small molecule, novel antiviral agent discovered by FUJIFILM Toyama Chemical Co., Ltd. It is a broad-spectrum antiviral that includes activity against all RNA virus families tested, including rabies, Ebola, Lassa, and coronaviruses. It has been in clinical trials for influenza, Severe Fever with Thrombocytopenia virus, Ebola, and has been used under compassionate release for Ebola, rabies, Lassa fever, norovirus, severe acute respiratory syndrome and the novel coronavirus 2 (SARS-CoV-2), the novel coronavirus that causes the coronavirus disease of 2019 (COVID-19).

There is a global pandemic caused by SARS-CoV-2, threatening the lives of many and resulting in the need for well-tolerated molecular agents to speed cessation of viral shedding and ultimately recovery from COVID-19. SARS-CoV-2 causes disease ranging from mild, cold-like symptoms to acute respiratory failure and death. Epidemiologic studies are underway to determine whether individuals can be asymptomatic and transmit disease. There is currently no available approved treatment for COVID-19. People who have been hospitalized to treat acute respiratory symptoms in the US have no proven option other than supportive care, which includes mechanical ventilation, oxygen therapy, and treatment of coinfections and organ failure if needed.

Evidence from nonclinical (cell culture) experiments and recently reported clinical experience in China indicates that favipiravir may have clinical benefit in subjects infected with SARS-CoV-2. Prior influenza research indicated faster cessation of viral shedding and faster recovery for subjects treated with favipiravir than with placebo control. The safety profile of favipiravir is well-established. It is generally safe and well-tolerated except for transient elevations of uric acid that resolve with cessation of dosing. The risk-to-benefit assessment of treatment with favipiravir in the face of COVID-19 is clearly in favor of potential study subjects.

This study will assess the time course of cessation of viral shedding and gather clinical benefit information in subjects with COVID-19 treated with favipiravir as compared to control. Data from this trial are expected to support the planning and execution of a larger study to demonstrate clinical benefit. The information gathered from this study will also help define the safety profile of favipiravir during the global pandemic and enable expansion into other subject populations such as those who have been exposed but who are not yet ill.

#### 1.1.2. Study Objectives

The primary objective of this study is to determine the effect of favipiravir plus standard of care (SOC) vs SOC on viral clearance.

The secondary objectives of the study are as follows:

- To determine the clinical benefit of administering favipiravir plus SOC compared to SOC alone (assessed using a study-specified 6-point ordinal scale adapted from the

World Health Organization [WHO] Master Protocol [V2.0 24FEB20] COVID-19 7-point ordinal scale) in adult subjects hospitalized with COVID-19.

- To determine if the treatment effect on the 6-point ordinal scale, on Day 15, is reasonably likely to reflect clinical benefit such that it can be used as the primary clinical outcome endpoint in a similar study that is double-blinded, by assessment of the relationship of the scale to changes in clinical and symptom outcomes, including time to clinical recovery, occurrence of fever, cough, dyspnea, reduction in oxygen requirements, and other measures.
- To explore the clinical effect of favipiravir + SOC vs SOC as measured by the National Early Warning Score 2 (NEWS2) system.
- To determine the safety of favipiravir plus SOC compared to SOC alone in this population.
- To explore the pharmacokinetics (PK) of this dose regimen of favipiravir in this subject population.

This statistical analysis plan (SAP) is designed to outline the methods to be used in the analysis of study data in order to answer the study objective(s). Populations for analysis, data handling rules, statistical methods, and formats for data presentation are provided. The statistical analyses and summary tabulations described in this SAP will provide the basis for the results sections of the clinical study report (CSR) for this trial.

This SAP will also outline any differences in the currently planned analytical objectives relative to those planned in the study protocol.

## **1.2. Study Design**

### **1.2.1. Synopsis of Study Design**

This study is an open label, randomized, SOC-controlled, multicenter Phase 2 study of favipiravir in hospitalized subjects with COVID-19. Subjects will be randomized within their study site and stratified by the severity of disease to receive either favipiravir + SOC or SOC alone.

Standard of care will be site-specific and based on what each site is currently using for treatment of hospitalized COVID-19 patients.

The dose regimen will be 1800 mg favipiravir twice daily (BID) plus SOC or SOC alone on Day 1 followed by 1000 mg BID favipiravir (800 mg BID for subjects with Child-Pugh A liver impairment) plus SOC or SOC for the next 13 days.

Subjects are planned to have 14 days of treatment and 46 days of follow-up.

### 1.2.2. Randomization Methodology

Subjects will be evaluated for eligibility during Day 1, prior enrollment in the study or starting treatment. The randomization procedure will be performed centrally using the electronic data capture (EDC) system, IBM Clinical Development.

Approximately 50 subjects are planned to be randomized at a 1:1 ratio to receive either favipiravir + SOC or SOC alone. Randomization will be stratified by site and severity of illness at enrollment. Severity of illness at enrollment will be graded (i.e., critical disease, severe disease, or mild/moderate disease) as follows:

- Critical disease:
  - Requires supplemental oxygen delivered by non-rebreather mask or high-flow cannula, OR
  - Requires use of invasive or non-invasive ventilation, OR
  - Requires treatment in an intensive care unit, use of vasopressors, extracorporeal life support (i.e., extracorporeal membrane oxygenation [ECMO]).
- Severe disease:
  - Evidence of pneumonia on chest x-ray or computed tomography (CT) scan, or chest auscultation (rales, crackles), OR
  - Peripheral capillary oxygen saturation ( $SpO_2$ )  $\leq$  93% on room air OR partial pressure of oxygen ( $PaO_2$ )/fraction of inspired oxygen ( $FiO_2$ )  $<$  300 mmHg, OR
  - Requires supplemental oxygen by nasal canula, simple face mask, or other similar oxygen delivery device.
- Mild/moderate disease:  $SpO_2 > 94\%$  and respiratory rate  $\leq 24$  breaths/min without supplemental oxygen

The randomization will target balance within stratum. This does not guarantee balance overall; however, utilizing a block size of 2, as well as with sufficient sample size within strata, balance will be approximately maintained while pooling across sites.

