1 SYNOPSIS

Title	Open Label, Randomized, Controlled, Phase 2 Proof-of-Concept Study of the Use of Favipiravir v. Standard of Care in Hospitalized Subjects with COVID-19
Design	This is an open label, randomized, controlled, multicenter Phase 2 proof-of-concept study of favipiravir in hospitalized subjects with COVID-19. Subjects will be randomized within their study site and stratified by the severity of their disease to receive either favipiravir + standard of care (SOC) or SOC alone.
	The dose regimen will be 1800 mg favipiravir BID plus SOC or SOC alone on Day 1 followed by 1000 mg BID favipiravir (800 mg BID for subjects with Child-Pugh A liver impairment) plus SOC or SOC for the next 13 days.
	The study will have 14 days of treatment and 46 days of follow-up.
Objectives	Primary Objective
	To determine the effect of favipiravir + SOC v. SOC on viral clearance.
	Secondary Objectives
	 To determine the clinical benefit of administering favipiravir plus SOC compared to SOC alone [assessed using a study-specific 6-point ordinal scale adapted from the WHO Master Protocol (V2.0 24FEB20) COVID-19 7-point ordinal scale] on Day 15 in adult patients hospitalized with COVID-19. To determine if the treatment effect on the 6-point ordinal scale, on Day 15, is reasonably likely to reflect clinical benefit, such that it can be used as the primary clinical outcome endpoint in a similar study that is double-blinded, by assessment of the relationship of the scale to changes in clinical and symptom outcomes, including time to clinical recovery, occurrence of fever, cough, dyspnea, reduction in oxygen requirements, and other measures. To explore the clinical effect of favipiravir + SOC v. SOC as measured by the National Early Warning Score 2 (NEWS2) system. To determine the safety of favipiravir plus SOC compared to SOC alone, in this population. To explore the PK of this dose regimen of favipiravir in this patient population.
Endpoints	Primary Endpoint:
	Time to viral clearance.
	Secondary Endpoints:
	1. Status of Clinical recovery as measured by the study-specific 6-point ordinal scale at Day 15.

- 2. Time to Clinical Recovery (TTCR) as assessed up to 29 days and defined as:
 - a. The time (in hours) from initiation of study treatment (favipiravir + SOC or SOC alone) until normalization of fever, respiratory rate, and oxygen saturation, and alleviation of cough, sustained for at least 72 hours; or discharge.
 - b. Normalization and alleviation criteria are defined as:

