 - i. Fever ≤ 37.2 °C oral,
 - ii. Respiratory rate ≤ 24 /minute on room air,
 - iii. Oxygen saturation SpO2 > 94% on room air,
 - iv. Cough mild or absent on a patient reported scale of severe, moderate, mild, absent.
- 3. Clinical effect as measured by the National Early Warning Score 2 (NEWS2) system.
- 4. All-cause mortality as assessed daily up to 29 days and at final follow up on Day 60.
- 5. Frequency of respiratory progression as assessed up to 29 days (daily and per SOC at each site) and defined as:
 - a. SpO2 \leq 94% on room air or PaO2/FiO2 \leq 300mmHg, and
 - b. requirement for supplemental oxygen, or
 - c. more advanced ventilator support.
- 6. Time to defervescence (in those with fever at enrollment) as assessed daily up to 29 days and at Day 60 (if possible).
- 7. Time to cough reported as mild or absent (in those with cough at enrollment rated severe or moderate) as assessed daily up to 29 days and on Day 60.
- 8. Time to dyspnea reported as mild or absent (on a scale of severe, moderate, mild absent, in those with dyspnea at enrollment rated as severe or moderate) as assessed daily up to 29 days and on Day 60 (if possible).
- 9. Frequency of requirement for supplemental oxygen or non-invasive ventilation as assessed daily up to 29 days and on Day 60.
- 10. Time to SARS-CoV-2 RT-PCR negative in upper respiratory tract specimen as assessed up to 29 days.
- 11. Change in SARS-CoV-2 viral load in upper respiratory tract specimen as assessed by area under viral load curve as assessed up to 29 days.
- 12. Frequency of requirement for mechanical ventilation as assessed up daily to 29 days and at Day 60
- 13. Safety of favipiravir + SOC v. SOC alone as assessed daily up to 29 days and at Day 60.
- 14. C-reactive protein (CRP) over time.
- 15. Population PK analysis of favipiravir with assessment of maximum plasma concentration (C_{max}), minimum plasma concentration (C_{min}), and AUC_(0-24h) on Days 1, 2, 8 and 14.

Study Sites	Approximately 8 sites in the U.S.A.
Planned Enrollment	Approximately 50 subjects; randomized 1:1
Study Population	Adults who are hospitalized for treatment of confirmed COVID-19

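### A fixed block size of 2 within site-by-severity strata, in an open-label trial, makes up to about 38–40% of allocations knowable in advance to site staff who know or infer it

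*SAP*

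**What the plan says.** The SAP's randomization section (1.2.2) states: "Randomization will be stratified by site and severity of illness at enrollment". Severity has three levels, "critical disease, severe disease, or mild/moderate disease", and balance is to be kept within stratum "utilizing a block size of 2". The same section gives the size and ratio ("Approximately 50 subjects are planned to be randomized at a 1:1 ratio") and the mechanism: "The randomization procedure will be performed centrally using the electronic data capture (EDC) system".

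The Protocol synopsis agrees on the structure ("Subjects will be randomized within their study site and stratified by the severity of their disease") and gives the number of sites ("Approximately 8 sites in the U.S.A"), but neither it nor the rest of the Protocol gives a block size. SAP 1.2.1 describes the masking: "This study is an open label, randomized, SOC-controlled, multicenter Phase 2 study".

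Neither document says that block sizes vary, or that the block size is withheld from sites. The only reason given for the choice is balance; predictability is not discussed.

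**The concern.** With blocks of 2, each completed pair in a stratum holds one subject per arm. Treatment is open label, so staff see the first assignment of a pair. Anyone who knows the block length then knows the second before deciding whether, or when, to enrol the next patient in that stratum.

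There is room to act on that knowledge. Protocol exclusion 14 leaves ineligibility to the investigator's judgement without further condition. The entry windows (72 hours from hospitalization, 10 days from symptom onset) allow some choice of timing. The Protocol's general statistical section (9.1) rests proof of concept on significance for time to viral clearance. A PCR endpoint limits bias in assessment, but not bias in who is enrolled to which arm.

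**Working it through.** **Inputs.** N = 50, 1:1, three severity levels and block size 2 (SAP 1.2.2); about 8 sites (Protocol synopsis). Strata: 8 × 3 = 24, so 50/24 ≈ 2.1 subjects per stratum. How subjects spread over strata is not stated and is assumed below.

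**The plan's own figure.** The documents give no figure for predictability. The only stated figure used here is the sample size. Medians of 4 and 11 days give a hazard ratio of 2.75 under exponential times. The mean clearance probability by Day 15 is 1 − ½(2^(−15/4) + 2^(−15/11)) = 0.769. At two-sided alpha 0.10 and 90% power, Schoenfeld's formula needs 34 events, so N = 45. Freedman's needs 39.3 events, so about 51, or 26 per arm. The stated 25 per arm lies between them.

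**Forced allocations, block of 2.** A stratum with n subjects has floor(n/2) forced allocations. With n ~ Binomial(N, w):

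E[floor(n/2)] = ½ [ N·w − ½(1 − (1 − 2w)^N) ]

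- Equal strata, w = 1/24: ½ [2.083 − ½(1 − 0.0129)] = 0.795 per stratum. Times 24 this is 19.1 of 50, or 38.2%. The 95% simulation range is 34% to 42%.
- Severity 20/60/20 with uneven sites (assumed): 19.6, or 39.3%.
- Severity 10/80/10 with uneven sites (assumed): 20.4, or 40.8%.
- Only two severity levels in use (25/75, assumed): 42% to 43%.
- Arithmetic limits: forced = (50 − number of strata with an odd count)/2. This lies between (50 − 24)/2 = 13 (26%) and 25 (50%).

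**Correct-guess rate.** Forced allocations are always guessed right and the rest half the time: f + (1 − f)/2. For f = 0.382 this is 0.69; for f = 0.408 it is 0.70.

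**If the block size must be inferred.** In simulation, only about 4 to 5 of the 24 strata ever reach two completed pairs, so a site has to pool its strata. Forced allocations that occur after a site has seen at least two completed pairs average 5.4 to 8.9 (11% to 18%). After at least three pairs they average 1.9 to 5.8 (4% to 12%). Two opposite pairs are weak evidence, since unrestricted 1:1 randomization gives them with probability ½ × ½ = ¼.

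**Alternatives, still 24 strata and N = 50.**

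| Block sizes | Structurally forced | SD of overall imbalance |
|---|---|---|
| Fixed 2 | 38–40% | about 3.2–3.4 |
| Fixed 4 | 13–18% | about 4.1–4.6 |
| Random 2/4 | 24–27% | not needed here |
| Random 2/4/6 | 16–19% | about 4.2–4.7 |

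For the random schemes the forced share counts allocations as if staff knew each block's length, so it is an upper limit. With the length of each block hidden, about 4% of allocations are certain under 2/4 (equal strata), and the best-guess rate is about 0.65.

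The imbalance for blocks of 2 can be checked by hand. Only odd strata contribute, one subject each, so with equal strata the SD is √(50 − 2 × 19.1) = √11.8 ≈ 3.4.

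**What exploitation could do (illustration only).** Assume no drug effect, an 11-day median in both arms, and every forced allocation steered so that the clearance hazard is multiplied by r on favipiravir and divided by r on SOC. The values of r are assumptions. Significant results favouring favipiravir rise from the nominal 5% to about 11–13% at r = 1.25 and 21–22% at r = 1.5.

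**The case against.** The strongest defence is that the choice has a purpose. At about two subjects per stratum, larger blocks are often left incomplete, and within-stratum balance loosens. Randomization is central, the Protocol that sites work from gives no block size, and the first member of each pair (about 60% of allocations) stays unpredictable. This is an exploratory study. All of that stands. It makes 38–40% a ceiling rather than an expected exposure, but it does not remove the pattern: a central system hides the list, not the assignments already made.

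Four stronger readings are tempting and are not supported.

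- A reader might infer that concealment is defeated outright. It is lost only for the second member of a pair, and only to someone who knows or infers the block size. The documents do not say whether sites are told it.
- A reader might infer that staff would see strict alternation. Blocks of 2 allow favipiravir–SOC followed by SOC–favipiravir, and few strata show enough pairs to make the pattern plain.
- A reader might infer selection bias beyond the reach of any analysis. Predictability is an opportunity, not evidence of bias. Comparing forced with unforced allocations could detect it, though not reliably correct it. The stratified log-rank sensitivity analysis (SAP 4.3.1) addresses differences between severity levels, not selection within one.
- A reader might add that cough, dyspnea and discharge are recorded with the arm known. That follows from open-label treatment and would be the same under any block size.

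**Conclusion.** The concern holds as an avoidable weakness in the design. Up to about 38–40% of allocations are certain to a site member who knows the block size and tracks strata. Exposure is roughly 11–18% if the size has to be inferred and two completed pairs are enough to infer it.

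The ceiling rests on 24 strata, 50 subjects and an assumed spread over strata; N of 45 to 55 with equal strata moves it only to 37–39%. The lower range also depends on how uneven recruitment is and how quickly staff would recognise the pattern. The false-positive illustration assumes full exploitation and is no estimate of what happened. The stated rationale of balance does not outweigh the weakness, because most of the balance can be kept at little cost.

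**What to change.** In SAP 1.2.2 and the EDC randomization list, replace the fixed block of 2 with randomly varying block sizes, for example 2, 4 and 6. State that the sizes are not disclosed to sites, and keep stratification by site and severity. A fixed block of 4 has a similar forced share, but its single length can be learned or inferred in the same way.

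The work is a regenerated list and a revised sentence. The statistical cost is about one more subject in mean absolute arm imbalance, plus somewhat looser within-stratum balance. Even an imbalance of about two SDs (2 × 4.7 ≈ 9, roughly 30 v. 20) keeps 4 × 30 × 20/50² = 96% of the efficiency of an even split.

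Dropping site as a stratification factor is not an equivalent remedy: it would contradict the Protocol's within-site randomization and need an amendment. Protocol 9.1 has the SAP completed after study initiation, so the list may already be in use. If so, apply the change to the remaining subjects and add the comparison of forced with unforced allocations as a sensitivity analysis.
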